- Net area under the curve (netAUC) of postprandial glucose as measured by CGM in the 6 hours following the start of first meal. netAUC (mg/dL*min) will be calculated using a trapezoidal method [76], which sums all CGM values in the 6 hour period following the meal above the starting glucose and subtracts CGM values below the starting glucose.
- Percent of time with sensed glucose <70 mg/dl
- Percent of time with sensed glucose between 70 – 140 mg/dl
- Mean sensed glucose
- Percent of time with sensed glucose <54 mg/dl
- Percent of time with sensed glucose >180 mg/dl
- Percent of time with sensed glucose >250 mg/dl
- Mean amount of insulin delivered (in units and units/kg)
- Mean amount of pramlintide delivered (in mcg and mcg/kg)
- Coefficient of variation
- LBGI
- HBGI
- Safety endpoints (over full study duration):
 - Adverse events
 - Number of adverse events probably or possibly associated with pramlintide administration (see ‘Causality Relationship’ below)
 - Baxter Retching Faces (BARF)/VAS scale for gastrointestinal issues after first and second meal, see Protocol Appendix D.
 - Mean duration of gastrointestinal issues after first and second meal as reported by participant on BARF/VAS scale, see Protocol Appendix D.
 - Episodes of carbohydrate intake to treat hypoglycemia (defined as 15g carbohydrate intake)
 - Episodes of hypoglycemia defined as CGM <70mg/dL for 10 minutes or more
 - Number of provider-administered insulin injections due to hyperglycemia

Study Type

This is a single-center, crossover trial designed to evaluate glucose outcomes of a fully closed-loop system with insulin+pramlintide dosed in response to meal detection as compared to an insulin alone fully closed loop system.

Study Population

Study population will be adults with type 1 diabetes, ages 18 – 70 years of age. Younger participants are excluded as it is appropriate to assess safety first in the over 18 year old population. We are targeting a total of 35 participants to complete the full study protocol.

[figure not shown]
Power Analysis

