basal insulin administration. Participants will wear a Polar M600 fitness watch to inform the controller about physical activity. The research staff will initialize the system, input insulin settings and begin the closed-loop study. See Appendix A for a picture of the closed-loop system. Two staff will review each of the settings to confirm the settings are entered correctly. Participant will receive training on using the iPancreas smart phone application. A member of the study staff will remain near to the participant for the duration of the study to address any alerts or issues that arise. The study investigator will be on call for the duration of the study.

The algorithm will push data up to an encrypted, secure Amazon Web Services cloud server that can be monitored remotely every 5 minutes. The iPancreas software will generate alerts on the smartphone. In order to push alerts to study coordinators and study investigators, the cloud server used for remote monitoring will have a drop down menu for study staff to sign in and out for the duration of their monitoring shift. Each study coordinator and investigator listed in the menu will have a cell phone number on the server that can receive texts with pushed alerts.

During all studies, sensed glucose data will be wirelessly transmitted via BTLE from the Dexcom G6 transmitter to the insulin-delivery algorithm every five minutes. The insulin-delivery algorithm will calculate insulin doses and will run on a Samsung smart phone. The smart phone will wirelessly communicate via BTLE to a PDM communicating to an Omnipod for automated insulin delivery. Participants will wear a Polar watch for collecting heart rate and accelerometry data. The Polar watch transmits this data to the smartphone controller via Bluetooth. iPancreas will convert the heart rate and accelerometry data into an estimated energy expenditure.

If at any time the study staff determines that a sensor can no longer be used, a new sensor will be inserted. If the participant's blood glucose is < 70 mg/dl or is experiencing symptoms of hypoglycemia, he/she will be instructed to treat with 15 grams of carbohydrates. Glucose tablets will be provided to the participants.

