The algorithm will push data up to an encrypted, secure Amazon Web Services cloud server that can be monitored remotely every 5 minutes. The iPancreas software will generate alerts on the smartphone. In order to push alerts to study coordinators and study investigators, the cloud server used for remote monitoring will have a drop down menu for study staff to sign in and out for the duration of their monitoring shift. Each study coordinator and investigator listed in the menu will have a cell phone number on the server that can receive texts with pushed alerts.

During all studies, sensed glucose data will be wirelessly transmitted via BTLE from the Dexcom G6 transmitter to the insulin-delivery algorithm every five minutes. The insulin-

delivery algorithm will calculate insulin doses and will run on a Samsung smart phone. The smart phone will wirelessly communicate via BTLE to a PDM communicating to an Omnipod for automated insulin and pramlintide delivery. Participants will wear a Polar watch for collecting heart rate and accelerometry data. The Polar watch transmits this data to the smartphone controller via Bluetooth. iPancreas will convert the heart rate and accelerometry data into an estimated energy expenditure.

If at any time the study staff determines that a sensor can no longer be used, a new sensor will be inserted. If the participant's blood glucose is < 70 mg/dl or is experiencing symptoms of hypoglycemia, the procedure noted below will be followed. Glucose tablets will be provided to the participants.

- o If CBG < 70 mg/dL occurs during pramlintide treatment visit:
 - Give 15 grams of oral carbohydrate.
 - Repeat treatment every 15 minutes with 15 grams oral carbohydrate as needed to raise blood glucose ≥ 70 mg/dl.
 - Repeat CBG checks every 15 minutes for 45 minutes to ensure glucose is persistently ≥ 70 mg/dl.

For participant safety, if communication is lost between the iPancreas app and the Dexcom G6 CGM for ≥ 20 minutes or the insulin pod ≥ 30 minutes, the insulin pump shall deliver basal insulin according to pre-set basal rates designated within the iPancreas settings according to given times of day and the pramlintide pump will deliver a fixed ratio of pramlintide to match the pre-set basal rate for insulin.

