The study will be terminated and the participant's own insulin pump or home basal insulin will be restarted. The study investigator will consult with the participant regarding appropriate insulin dosing for the remainder of the day, considering pramlintide on board as tracked by the iPancreas system. If this level is elevated,, the participants will be offered an additional meal to eat before they discharge. The study investigator will consult with the participant in regards to a safe mealtime insulin dose given from their home pump or insulin pen.

The Polar watch and Omnipods will be removed from the participant. The participants will wear Dexcom sensor until just prior to discharge to track the glucose and trend arrow. Participants will complete a pictorial nausea rating scale (the Baxter Retching Faces [BARF] scale), if applicable (see Protocol Appendix D)[78]. All infusion and sensor sites will be inspected for signs of irritation or infection. In addition, the sensor will be inspected for the possibility of breakage or fracture. If there is any evidence of sensor breakage, it will be recorded. If an area of inflammation of 1 cm or greater exists around the point of insertion, a de-identified photograph will be taken of the area and the participant will return 1-3 days later for a follow-up visit. A capillary blood glucose value will be measured. Participants will be given oral carbohydrate for values below 85 mg/dl with a repeat capillary blood glucose every 15 minutes until glucose is \geq 85 mg/dL. If capillary blood glucose is greater than 180mg/dL, participants will be instructed to take a correction bolus from their home insulin pump or via home insulin pen/vial per their usual home settings after reviewing this dose with the study investigator who will modify dose if needed considering current insulin on board.

If the initial capillary blood glucose was > 85 mg/dL, the participant can then be discharged home if the next capillary blood glucose measurement 30 minutes later is less than 300 mg/dL or if the CGM glucose trend arrow shows flat arrow (increasing/decreasing less than 1 mg/dL each minute) or a down arrow (decreasing >30 mg/dL in 30 minutes). If the initial capillary blood glucose was < 85 mg/dL, then the participant will be given oral carbohydrates and we will repeat a fingerstick every 15 minutes until glucose is ≥ 85 mg/dL and the CGM trend arrow is flat or trending up, then patient can be discharged.

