Participants who will be taking an NPH dose prior to discharge from the clinic and who currently do not use a CGM or are not actively using their personal CGM will continue to use the study CGM for approximately 12 hours after the visit completes. Study staff will complete a phone check-in the next day to remove the CGM. The participants will be asked to check glucose from CGM at 2am the morning after their treatment visit. If the CGM value is above 150 mg/dl, participants will be asked to take 80% of the correction bolus. If the glucose is less than 100 mg/dL they will be instructed to take 15 grams of carbohydrate.

Participants will be given a snack to take with them for the trip home. Participants will also be advised to monitor their glucose for any symptoms of hyperglycemia or hypoglycemia, before

their next meal, and at bedtime. Study staff will call the participant approximately 1 hour after discharge and participant will obtain a fingerstick glucose at that time.

If a study visit is stopped prematurely, such as due to technical problems, the participant will be asked if they can repeat the study visit that was terminated early with additional compensation provided. Repeating the study visit will be optional.

Adverse Events

Causality relationship to Pramlintide administration

The causality of each AE should be assessed by the Investigator according to the following classification:

Probable: Good reason and sufficient documentation to assume a causal relationship.

Possible: A causal relationship is conceivable and cannot be dismissed.

Unlikely: The event is most likely related to etiology other than the pramlintide administration.

Not related: The event occurs before any pramlintide has been started.

Table 1: Schedule of Events

Automated insulin delivery system abbreviated AID

¹ ins/pram visit

	Screening	Active Treatment		End of Treatment
Description of visit procedures	Screening visit	Dexcom CGM insertion visit	1st AID visit	2nd AID visit
Visit Number	1	2	3	4
Visit Window		1-84 days	1-8 days	3-28 days
Informed Consent	X			
Medical history/	X	X	X	X
Focused physical	X			
Eligibility assessment	X			
Download data from participant's existing insulin pump and glucose sensor (if applicable)	X			
Review medications and doses	X	X	X	X
Hypoglycemia awareness survey	X			
Measure BP, pulse, height and weight	X			
Pregnancy Test (Urine)	X	X	X	X
Hemoglobin A1c	X			
Complete Blood Count (CBC)	X			
Comprehensive Metabolic Panel (CMP)	X			

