Adverse Event Reporting		X	X	X
Dexcom G6 CGM and iPancreas usage training		X		
Examination of sensor site after removal (if applicable)			X	X

Hypoglycemia Treatment Guidelines**CBG < 70 mg/dl**

- Give 15 grams of oral carbohydrate.

- Repeat treatment every 15 minutes as needed to raise blood glucose ≥ 70 mg/dl.
 - o If CBG < 70 mg/dL occurs during pramlintide treatment visit:
 - Give 15 grams of oral carbohydrate.
 - Repeat treatment every 15 minutes with 15 grams oral carbohydrate as needed to raise blood glucose ≥ 70 mg/dl.
 - Repeat CBG checks every 15 minutes for 45 minutes to ensure glucose is persistently ≥ 70 mg/dl.

Presence of STUPOR, LOSS OF CONSCIOUSNESS, or SEIZURE

- Give 3 mg glucagon intranasal
- Verify that insulin and pramlintide are turned off.

Hyperglycemia Treatment Guidelines

If the sensed glucose is ≥ 300 mg/dl, the participant will be instructed to check their blood glucose and to check the Omnipod for malfunction. This would include checking for insulin leaks, making sure Omnipod is securely adhered to skin, and check for error messages on the phone running the algorithm.

If capillary blood glucose value is over 300 mg/dl for more than 2 hours or is ≥ 400 mg/dl at any time, the participant will be instructed to check serum ketones using the Abbott Precision Xtra meter and to change out the Omnipod. If serum ketones are over 0.6 mM, the participant will be instructed by study investigator to discuss proper management, including delivering a correction bolus. In addition, the participant will be encouraged to drink sugar-free liquids. If serum ketones are above 1.5 mM at any time, the study will be stopped and insulin will be administered as directed by the on call investigator.

Cleaning and Disinfecting

All devices will be cleaned and disinfected between participants. The smart phone, Polar watch and Omnipod PDMs are cleaned by study staff. Technicians who are disinfecting units will wash hands thoroughly and wear gloves. All items will undergo intermediate-level disinfection using Oxivir TB disposable wipes. The disinfectant will be applied and allowed to air dry. After disinfection, when the units are completely dry, they will be placed in a sealed bag labeled with participant information.

Stopping Rules

Individual study stopping rules

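### The count of carbohydrate treatments has no rule for merging repeats, and fingerstick rechecks after a low are scheduled at the pramlintide visit only, so that arm's count can rise for the same glucose

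*Combined protocol and SAP*

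**What the plan says.** **Counting unit.** The safety endpoints, under Secondary Endpoints, include "Episodes of carbohydrate intake to treat hypoglycemia (defined as 15g carbohydrate intake". They are to be measured over the full study duration. Neither that list nor Statistical methods says whether several treatments of one low are joined. The next line in the list is a separate endpoint: CGM below 70 mg/dL for at least 10 minutes.

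**Both visits.** Hypoglycemia Treatment Guidelines gives a general rule after the first 15 g: "Repeat treatment every 15 minutes as needed to raise blood glucose ≥ 70 mg/dl". It is not limited to one arm.

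**Insulin visit.** For glucose below 70 mg/dL or symptoms, Insulin Treatment Visit says "he/she will be instructed to treat with 15 grams of carbohydrates". It gives no recheck schedule.

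**Pramlintide visit.** Both Insulin + Pramlintide Treatment Visit and the guidelines add a block that opens "If CBG < 70 mg/dL occurs during pramlintide treatment visit". It repeats the 15 g rule and then adds "Repeat CBG checks every 15 minutes for 45 minutes to ensure glucose is persistently" at or above 70 mg/dL.

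**Discharge.** Both visits give carbohydrate for a fingerstick below 85 mg/dL. Only the pramlintide visit continues "with a repeat capillary blood glucose every 15 minutes until glucose is" at or above 85 mg/dL, and only that visit adds "Study staff will call the participant approximately 1 hour after discharge and participant will obtain a fingerstick glucose at that time". Both discharge sections begin by terminating the study.

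**The concern.** If the unit is one 15 g intake, the count depends on how often someone checks as well as on how often glucose is low. One arm has more scheduled checks after each treated low, and each can produce a reading below 70 mg/dL and another counted treatment.

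The Risks section says that pramlintide can make hypoglycaemia after a meal more likely, and safety is part of the first primary objective. An excess of treatments at the pramlintide visit would be read as a drug effect. As the endpoint stands, such an excess could not be divided into drug effect, extra checking and repeat counting. Slower gastric emptying on pramlintide, which the background describes, could also cause real repeat treatments, and the count could not tell these apart either.

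**Working it through.** **Plan's own figures.** The plan gives none for this endpoint. Its only power figures concern the primary comparison (35 participants, paired t test, two-sided 0.05). The noncentral t distribution with 34 degrees of freedom and noncentrality d × √35 gives 89.6% at d = 0.56 and 80.4% at d = 0.49, against the stated 90% and 80%. Nothing below enters those figures.

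**Step 1: the unit.** A low still below 70 mg/dL at 15 and 30 minutes is treated at 0, 15 and 30 minutes. That is 3 counts on the literal reading and 1 CGM-defined episode. The general guideline makes this true at both visits, so it explains why the count is sensitive to checking but gives no difference between arms.

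**Step 2: extra checks.** Checks every 15 minutes for 45 minutes number 45/15 = 3. Repeating treatment until 70 mg/dL is reached implies a 15-minute recheck at either visit.
- If the 45 minutes run from treatment, the checks fall at 15, 30 and 45 minutes. The first is common to both arms, so two are extra.
- If they run from the first recovered reading, all three are extra.

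The text does not say which.

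**Step 3: chance of a further count.** Let p be the chance that an extra check reads below 70 mg/dL. I assume p = 5% to 15% and independent checks; the documents give no value. The chance of at least one further count is 1 − (1 − p)^m for m extra checks.

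| Extra checks m | p = 5% | p = 15% |
|---|---|---|
| 2 | 1 − 0.95² = 9.8% | 1 − 0.85² = 27.8% |
| 3 | 1 − 0.95³ = 14.3% | 1 − 0.85³ = 38.6% |

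These are upper values, because they suppose that the insulin visit finds none of the same relapses.

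**Step 4: allowing for detection at the insulin visit.** Let r be repeat treatments per low common to both visits, s the later readings below 70 mg/dL per low found by the extra checks, and d the share of those that the insulin visit would find and treat anyway. For identical glucose, the pramlintide-to-insulin ratio of counts is (1 + r + s)/(1 + r + s × d). I assume s = 0.1 to 0.4. For comparison, 2 × 0.05 = 0.10 and 3 × 0.15 = 0.45.

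| d (with r = 0) | s = 0.1 | s = 0.4 |
|---|---|---|
| 0 | 1.10/1.00 = 1.10 | 1.40/1.00 = 1.40 |
| 0.5 | 1.10/1.05 = 1.05 | 1.40/1.20 = 1.17 |
| 0.8 | 1.10/1.08 = 1.02 | 1.40/1.32 = 1.06 |
| 1 | 1.00 | 1.00 |

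With r = 0.3 and d = 0 the ratio runs from 1.40/1.30 = 1.08 to 1.70/1.30 = 1.31.

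**Step 5: after merging.** If all treatments within one low and its recheck period count as one episode, a low treated k times scores 1 in either arm. The ratio for identical hypoglycaemia returns to 1.00, provided the merging interval spans the whole recheck period.

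**The case against.** The strongest reply is that the endpoint counts treatments by design. Hypoglycaemic episodes have their own line directly below, so 3 against 1 is two measures answering two questions. That is fair, and the endpoint is not wrong for counting treatments. But the plan calls them episodes and gives no merging rule. The 15 g could also be meant as a minimum per episode, although nothing says so. Two analysts could obtain different counts from the same data.

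A second reply is that the insulin visit would find most relapses. CGM alerts are set at 70 mg/dL, CGM data arrive every 5 minutes, and staff are close by at both visits. This stands, and it limits the size: at d = 0.8 the illustrative excess is 2% to 6%.

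A third is that the plan already lists CGM-defined episodes, time below 70 and 54 mg/dL, and LBGI, measured alike in both arms, while Statistical methods names no test for the carbohydrate count. This also stands. It makes the CGM measures the better basis for comparison but leaves the count unrepaired. Nor are the CGM measures wholly insulated, since extra carbohydrate in one arm can shorten its CGM lows.

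A reader might infer three stronger things that the documents do not support:
- **That counting repeats favours the insulin arm by itself.** Repeat treatment to 70 mg/dL is a rule for both visits.
- **That the discharge rechecks and the phone call add counts.** Both come after the study is terminated. Carbohydrate at 70-84 mg/dL is not clearly treatment of hypoglycaemia when the guideline threshold is below 70, and no 15 g amount is stated for it. The call asks for a fingerstick and mentions no carbohydrate.
- **That three extra checks per low are certain.** Two is equally consistent with the text.

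**Conclusion.** The point holds as a possible bias in one secondary safety count. The literal unit is one 15 g intake, post-treatment rechecks are scheduled at the pramlintide visit only, and nothing in Statistical methods corrects for the combination. The direction is towards more counted treatments on pramlintide for the same glucose.

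The size cannot be computed from the documents. The range of about 10-39% per treated low rests on an assumed 5-15% per check, independent checks, and no detection of the same relapses at the insulin visit. It falls towards zero as that detection improves. It should not be read as the expected excess in the trial.

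The primary endpoint definitions and the sample size do not depend on this count. A correction is still worth making, because the count bears on a risk that the protocol itself names and the remedy is mostly wording.

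**What to change.** - **Define the episode.** Count as one treated episode all carbohydrate given until a fixed treatment-free interval has passed that fully spans the recheck period. If the 45 minutes run from treatment, 60 minutes would serve; a strict 45 can miss a treatment given at or just after the last check. If they run from the first recovered reading, the last check falls 15 + 45 = 60 minutes after treatment, so the interval must exceed 60. State which applies.
- **Keep the detail.** Report the number of 15 g treatments and total rescue grams separately. The merged count no longer shows repeat treatments, and this report preserves them.
- **Bound the window.** Count from closed-loop start to closed-loop stop in both arms, which settles the discharge question.
- **Name the comparison.** Base the between-arm comparison of hypoglycaemia on the CGM-defined episodes already listed, and read the treatment counts beside them.
- **Reconcile or acknowledge.** The recheck text in Insulin Treatment Visit, Insulin + Pramlintide Treatment Visit and Hypoglycemia Treatment Guidelines, and in the two discharge sections, should be reconciled, or the difference stated as a limitation of this count. I take no view on which clinical schedule is right.

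The first four items need only endpoint and analysis wording, with no new data beyond the time and amount of each treatment. The last costs a sentence if the difference is acknowledged.

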$$\text{Total Insulin Bolus} = \frac{\text{Carbohydrate (g)}}{\text{Carbohydrate Ratio}} + \frac{\text{Current glucose} - \text{Target Glucose}}{\text{Correction Factor}} - \text{IOB}$$

Discharge from inpatient clinic

The study will be terminated and the participant's own insulin pump or home basal insulin will be restarted. The study investigator will consult with the participant regarding appropriate insulin dosing for the remainder of the day. The Polar watch and Omnipod will be removed from the participant. The participant will wear Dexcom sensor until just prior to discharge to track the glucose and trend arrow. Participants will complete a pictorial nausea rating scale (the Baxter Retching Faces [BARF] scale), if applicable (see Protocol Appendix D)[78]. All infusion and sensor sites will be inspected for signs of irritation or infection. In addition, the sensor will be inspected for the possibility of breakage or fracture. If there is any evidence of sensor breakage, it will be recorded. If an area of inflammation of 1 cm or greater exists around the point of insertion, a de-identified photograph will be taken of the area and the participant will return 1-3 days later for a follow-up visit. A capillary blood glucose value will be measured. Participants will be given oral carbohydrate for values below 85 mg/dL, and if capillary blood glucose is greater than 180mg/dL, participants will be instructed to take a correction bolus from their home insulin pump or via home insulin pen/vial per their usual home settings after reviewing this dose with the study investigator who will modify dose if needed considering current insulin on board. The participant can then be discharged home if the next capillary blood glucose measurement 30 minutes later is less than 300 mg/dL or if the CGM glucose trend arrow shows flat arrow (increasing/decreasing less than 1 mg/dL each minute) or a down arrow (decreasing >30mg/dL in 30 minutes).

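### The insulin-visit discharge rule treats values below 85 mg/dL but sets no recovery value, so a participant at 70–84 mg/dL and falling satisfies it

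*Combined protocol and SAP*

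**What the plan says.** The combined protocol and SAP has a separate subsection, Discharge from inpatient clinic, for each treatment visit.

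**Insulin Treatment Visit.** A capillary glucose (CBG) is measured. "Participants will be given oral carbohydrate for values below 85 mg/dL, and if capillary blood glucose is greater than 180mg/dL", a correction bolus follows, reviewed with the investigator. The release test comes next: "discharged home if the next capillary blood glucose measurement 30 minutes later is less than 300 mg/dL or if the CGM glucose trend arrow" is flat or down, a down arrow being a fall of more than 30 mg/dL in 30 minutes. No value has to be reached after carbohydrate. The sensor stays on: "The participant will wear Dexcom sensor until just prior to discharge to track the glucose and trend arrow".

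**Insulin + Pramlintide Treatment Visit.** A general sentence says: "Participants will be given oral carbohydrate for values below 85 mg/dl with a repeat capillary blood glucose every 15 minutes until glucose is" at least 85 mg/dL. Two branches follow. For a higher start, "If the initial capillary blood glucose was > 85 mg/dL, the participant can then be discharged home" on the same test as at the insulin visit. For an initial value below 85, fingersticks are repeated every 15 minutes until at least 85 mg/dL "and the CGM trend arrow is flat or trending up, then patient can be discharged".

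**Elsewhere.** During the insulin visit a participant with glucose below 70 mg/dL "or is experiencing symptoms of hypoglycemia, he/she will be instructed to treat with 15 grams of carbohydrates". The Hypoglycemia Treatment Guidelines repeat treatment until at least 70 mg/dL.

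**The concern.** The insulin-visit test has an upper limit and no lower one, its conditions are joined by *or*, and falling glucose is itself a ground for release. That is sensible when a correction bolus has been given and the question is whether a high value is coming down. It is the wrong question when the value is low.

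At stake is safety on the way home. By then the study pod is being removed, the home pump or basal insulin restarted, and some participants given NPH before leaving. On the protocol's timeline the last scheduled meal was about six hours earlier. A participant treated for a value below 85 may leave without anyone having confirmed that the treatment worked.

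**Working it through.** The plan gives no figure to reproduce here, so the check applies the rules as written to example cases.

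**Inputs.** Insulin-visit discharge: carbohydrate below 85; release if the 30-minute CBG is below 300, or the arrow is flat or down. Pramlintide-visit discharge: the general sentence and two branches described above. Hypoglycemia Treatment Guidelines: below 70, treat until at least 70.

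**Step 1: the affected band.** Every value below 85 is also below 300, so the insulin-visit test excludes no low value, whatever the arrow. The guideline supplies the only other numeric floor, 70. The band that is treated but not held is therefore 70–84 mg/dL.

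**Step 2: cases** (CBG in mg/dL).

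| Initial CBG, 30-min CBG, arrow | Insulin visit as written | Pramlintide visit as written | Insulin visit after the fix |
|---|---|---|---|
| 75, 78, down | release | hold | hold |
| 75, 85, flat | release | release | release |
| 100, 75, down | release | branch releases; general sentence can be read to hold | hold |
| 85, 80, down | release | neither branch applies | hold |
| 100, 90, flat | release | release | release |
| 116, 86, down | release | release | release |
| 260, 220, down, after bolus | release | release | release |
| 320, 310, flat, after bolus | release | release | release |

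The fix changes only the cases with a discharge value below 85 that have not recovered.

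**Step 3: routes into the band.** A participant may already be there at the first reading. Otherwise, a 30 mg/dL fall over the 30 minutes leads there from initial values of 70 + 30 = 100 to 84 + 30 = 114. The discharge correction bolus is not a realistic route: from above 180 to 84 is a fall of more than 180 − 84 = 96 mg/dL, or more than 96/30 = 3.2 mg/dL per minute.

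**Step 4: speed, as an outer bound only.** A down arrow means more than 30/30 = 1 mg/dL per minute. At a constant rate with no carbohydrate, 84 reaches 70 within (84 − 70)/1 = 14 minutes. The protocol does give carbohydrate below 85, so this is not the expected course. The discharge text states no carbohydrate amount, and the documents give no glucose rise per gram, so the treated course cannot be calculated.

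**The case against.** The strongest reply is that nobody in this band is meant to leave untreated. The carbohydrate instruction refers to values in the plural, so its plain reading covers the recheck as well as the first reading. A reader might infer that the plan sends participants home low, falling and untreated; the text does not support that. What stands is narrower: carbohydrate is given, but recovery is not confirmed.

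Second, the stricter pramlintide rule may reflect pramlintide's own risk. The protocol describes delayed gastric emptying and more hypoglycemia after meals. It adds 45 minutes of repeat checks after a low value, a call about one hour after discharge and, if pramlintide on board is elevated, "the participants will be offered an additional meal to eat before they discharge". So the pramlintide rule does not prove that the sponsor holds 85 mg/dL with a flat or rising arrow to be the minimum for insulin alone. It does show that a workable hold is already written. Separately, the insulin-visit section suspends insulin during a communication loss when a sensor value of 70–140 is predicted to fall below 90 within 30 minutes. The plan thus treats low and falling glucose as a hazard without pramlintide too.

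Third, other safeguards exist:
- the sensor until just before discharge, and investigator advice on dosing;
- a snack and self-monitoring advice;
- exclusion of hypoglycemia unawareness and of recent severe hypoglycemia;
- for NPH takers, a 2 am check, plus the study sensor for about 12 hours if they have no active personal one.

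The release wording is also permissive, so staff may keep a falling participant. All of this lowers the risk; none of it sets a glucose value for discharge.

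Finally, the test may have been meant only for the period after a correction bolus. On that reading a participant with a low value has no stated discharge criterion at all, so a recovery value is still missing.

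**Conclusion.** The point holds for the insulin visit. Followed literally, the rule releases a participant at 70–84 mg/dL and falling, including one just given carbohydrate. This rests on reading the test as applying whatever the initial value, and on the general guideline applying up to discharge.

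Three stronger readings are not supported:
- **That the pramlintide visit has the same clear gap.** It is explicit and adequate for an initial value below 85. For a higher start its general sentence can be read to hold a low recheck. An initial value of exactly 85 falls in neither branch. These are minor wording points.
- **That a down arrow should bar discharge at any value, or that 300 mg/dL or more with a flat arrow should be held.** The pramlintide visit's own branch for a higher start allows both, and neither is part of this defect.
- **That the trial's results are at risk.** Discharge follows the closed-loop period, and the endpoints are not affected.

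The frequency is unknown, because the documents give none. It is a cheap improvement to participant safety, not a flaw in the trial's validity.

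**What to change.** **Insulin visit.** If the initial or the 30-minute discharge CBG is below 85 mg/dL, apply the hold already written for the pramlintide visit: oral carbohydrate and a CBG every 15 minutes until at least 85 mg/dL with a flat or rising arrow. Let the existing test (below 300, or a flat or down arrow) apply only when no discharge CBG is below 85. A down arrow alone then never releases a participant with a low value.

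**Pramlintide visit, minor clarification.** State that the same hold covers the 30-minute recheck, and change the first branch from > 85 to ≥ 85.

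**Cost.** A few sentences of protocol wording and, occasionally, a longer stay before discharge. Release after a correction bolus is unchanged whenever no discharge value is below 85.
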